1.0 PROTOCOL SUMMARY AND/OR SCHEMA

The primary objective of the study is to determine the maximum tolerated dose (MTD) of rucaparib in combination with breast and nodal radiotherapy (RT) in women with triple negative breast cancer (TNBC) with residual disease following neoadjuvant chemotherapy or high grade hormone receptor (HR) positive disease with high volume residual following neoadjuvant chemotherapy. Secondary objectives are to describe the toxicities and disease outcomes and to identify biomarkers of locoregional relapse following rucaparib plus RT.

[figure not shown]
This is an amended protocol in which we add additional negative dose escalation levels to allow probing of the MTD into lower doses of rucaparib. In the original design, we had one -1 dose level, but we have exceeded the observed DLT for the TITE-CRM threshold at this level (see Biostatistics, section 14). We now add 3 additional de-escalation (-2, -3, and -4 dose levels). It is not surprising that even low dose levels of a PARP inhibitor may have radiosensitizing effects; for this reason we add 3 additional de-escalations.

Eligibility criteria include stage I-III TNBC patients with residual invasive disease following neoadjuvant chemotherapy (NAC), as well as high grade HR positive disease with high volume residual (4 or more positive axillary nodes, or 5 cm or more of residual breast disease) after NAC. Tumor tissue will be collected at the time of surgery, if available, precluding the need for an extraneous biopsy.

Treatment will consist of rucaparib at one dose level (200 mg QD, 300 mg QD, 200 mg BID, 300 mg BID, 400 mg BID, 500 mg BID, 600 mg BID) throughout a 6-week course of RT and then 4 weeks of maintenance rucaparib, at the same dose level, following RT. RT dose will consist of 50 Gy in 2 Gy/fraction to the breast or post-mastectomy chest wall, with or without nodes plus a 10 Gy boost to the lumpectomy cavity or (optionally) to the mastectomy scar (total dose 60 Gy). Patients will be followed for evaluation of toxicity with weekly assessments during the 10-week study period. For post-mastectomy patients not treated with a boost (ie only 5 weeks of radiation), rucaparib will be continued for 4 weeks post-RT for a total of 9 weeks. Patient-reported outcomes will be assessed and subject drug diaries will be maintained. Patients will then be followed every 3-6 months for two years, as per standard follow-up care.

The trial will be monitored using a TITE-CRM (Time-To-Event Continual Reassessment Modulation) design¹. The target rate for dose-limiting toxicity (DLT) is 30%. DLT will be defined as toxicities probably or definitely related to the study drug observed during the study period. A detailed definition of dose-limiting toxicity (DLT) for this trial is defined in Section 9.5.

The target accrual is 30 patients, to be accrued within 2 years.

- Radiation dose is 50 Gy/25 fractions to the whole breast or chest wall +/- regional nodes plus a 10 Gy/5 fractions boost to the lumpectomy cavity. Mastectomy patients may also receive scar boosts; rucaparib will continue for 4 weeks post-RT (total of 9-10 weeks depending on whether a boost is used).
- Tumor tissue will be procured from the lumpectomy or mastectomy specimens, as well as from the baseline diagnostic cores, if available.

2.0 OBJECTIVES AND SCIENTIFIC AIMS

- The primary objective is to determine the maximum tolerated dose of rucaparib that can be administered concurrently with standard doses of radiotherapy to the breast/chest wall +/- regional nodes.
- Secondary objectives are:
 - To describe the nature of toxicity that develops when rucaparib is administered concurrently with RT.
 - To assess locoregional relapse and distant relapse.
 - To evaluate biomarkers (HRD status) correlated with locoregional relapse following rucaparib administered concurrently with RT.
 - To evaluate the presence of tumor infiltrating lymphocytes (TILs) and correlate this with locoregional relapse.
 - To assess patient reported satisfaction and quality of life with treatment using the Breast Cancer Treatment Outcomes Scale (BCTOS)
 - To determine the rate of poor cosmetic outcomes from both provider and patient perspectives up to 2 years after rucaparib + RT using the RTOG (Radiation Therapy Oncology Group) cosmesis scale² and digital images.

3.0 BACKGROUND AND RATIONALE

Triple negative breast cancer (TNBC), defined as estrogen receptor and progesterone receptor levels <1% and HER2-negative (0-1 + by immunohistochemistry or HER2/CEP17 ratio <2 or HER2 signals/cell <4 by in-situ hybridization constitutes 10-15% of breast cancers, but is disproportionately associated with rapid growth, early locoregional recurrence and metastasis and unfavorable prognosis compared to other subtypes of breast cancer³. TNBCs are characterized by a genomic profile that is similar to BRCA1-mutation carriers, indicative of defects in the BRCA pathway⁴. Although rarely mutated in sporadic breast cancer, BRCA1 expression has been reported to be reduced in a small number of sporadic tumors, particularly in TNBC⁵⁻⁷. BRCA1 and BRCA2 are only two of many proteins involved in executing homologous recombination repair (HRR)⁸. A subset of sporadic breast cancers may also have defects in HRR, in the absence of mutations in either BRCA1 or BRCA2^{9,10}. The frequency of BRCA1-BRCA2-RAD51 pathway defects in breast cancer has been quantified in 60 invasive breast cancer patients using an HRR assay developed at Memorial Sloan-Kettering Cancer Center. The incidence of HRR deficiency was the highest among TNBC patients (48%), compared to other subtypes (29% in HER2+, 21% in ER+)¹¹.

3.1 Rationale of Rucaparib plus Radiation Therapy

PARP is an enzyme involved in repair of endogenous or RT-induced single strand breaks (SSB). Inhibition of that pathway by a PARP inhibitor results in the accumulation of large amounts of SSBs, which can be converted to DSBs. In HRR-proficient cells, these DSBs are repaired by homology-directed repair. In HRR-deficient cells, however, such as cells with loss of BRCA1, BRCA2 or other proteins involved in the complex BRCA1-BRCA2 pathway, the repair machinery of the cell can be overwhelmed, leading to error-prone repair by alternative mechanisms. Inhibition of homologous recombination or PARPs may be well tolerated in isolation, but combined inactivation of these distinct DNA-repair pathways can result in cell death through synthetic lethality. In addition to its role in DNA repair, PARP has been shown to play a role in mitosis, where its inhibition has been proposed to lead to chromosome segregation errors, aneuploidy and in some cases, mitotic cell death¹²⁻¹⁴. Although chemotherapy and RT are common treatments for TNBC, there are no effective biomarkers that can reliably predict the sensitivity of these tumors to these treatments. By assaying the function of the HRR pathway using a combination of genomic and functional metrics, we aim to increase the accuracy of identifying TNBC patients who would maximally benefit from DNA repair-based therapies.

Given their mechanism of action, there is considerable interest in the potential of PARP inhibitors as radiation-sensitizing agents. In preclinical models, BRCA1 and BRCA2-deficient cells have been shown to be sensitive to PARP inhibitors. However, clinical studies utilizing PARP inhibitors in unselected sporadic TNBC have failed to show benefit of PARP inhibitors in improving progression-free survival¹⁵. There is scant data on locoregional outcomes following PARP inhibitor and RT.

Recently, a Phase I trial of veliparib and post-mastectomy RT in breast cancer patients with locally recurrent or inflammatory breast cancer reported dose-limiting toxicities in 4/30 patients¹⁶. Four dose levels of veliparib were tested (50 to 200 mg BID) with concurrent RT to the chest wall and nodes (50 Gy). Severe acute toxicity did not exceed 30%, even at the highest tested dose of veliparib (200 mg BID). Using these findings, the planning of a phase II trial testing the efficacy of veliparib and RT in breast cancer patients is currently in development. These findings underscore the importance of additional studies assessing the safety of PARP inhibitors with RT.

In a recently published series of 233 women with clinical Stage II-III breast cancer who underwent neoadjuvant chemotherapy (NAC), mastectomy and post-mastectomy RT at MSKCC, the rate of pathologic complete response (pCR) in TNBC patients was only 23%¹⁷. Failure to achieve pCR resulted in a higher 5-year locoregional recurrence rate compared to patients with HER2+ and hormone receptor-positive breast cancer (26% vs. 7% and 4%, $p<0.001$). Moreover, others have demonstrated the residual disease after neoadjuvant chemotherapy in TNBC is associated with significantly worse progression-free and overall survival¹⁸. The single notable effort to escalate therapy in these patients was recently reported by Masuda et al¹⁹ in the *New England Journal of Medicine*. In this phase III randomized trial, patients with incomplete responses after neoadjuvant chemotherapy were randomized to consolidation capecitabine vs null. Overall survival was longer in the capecitabine group. Although the trial was for all comers, the greatest improvement was seen in TNBC cases (OS 79 vs 70% at 5 years). Taken together, these results demonstrate the need for additional treatment intensification in TNBC patients with residual disease after neoadjuvant chemotherapy. Recently, the Keynote-522 has altered the landscape of early TNBC, and is a seminal trial that randomized 1174 women receiving NAC for early TNBC to either chemotherapy alone or with pembrolizumab 200 mg/m² every 3 weeks (2:1) (Schmid NEJM). Among the first 602 patients randomized, the pathological complete response rate (primary endpoint) was higher in the pembro arm (64.8%) compared to placebo (51.2%). The co-primary endpoint of event-free survival was also better with pembro, 91.3% vs 85.3%. These effects appeared to independent of PDL-1 status.

3.2 Study Disease: TNBC Residual Invasive Disease after NAC and BCS

TNBC patients who achieve less than a pCR to NAC are an ideal target population for combination treatments of PARP inhibitor and RT because: 1) effective locoregional therapies in such patients are lacking 2) RT is routinely indicated in such patients for enhancement of local disease control 3) the prevalence of HRR deficiencies in TNBC is high.

Rucaparib (CO-338) is a small molecule inhibitor of poly (adenosine diphosphate [ADP]-ribose) polymerase (PARP) being developed for cancers associated with homologous recombination deficiency (HRD). Rucaparib has been shown to potently inhibit PARP-1, PARP-2, and PARP-3 and has demonstrated activity in a background of breast cancer gene 1 and 2 (*BRCA1* and *BRCA2*) mutations in both clinical and nonclinical studies.

Rucaparib doses have been based upon review of the existing trials with rucaparib and the recommended starting dose for continuously administered oral monotherapy (600 mg BID). Timing of rucaparib administration in relation to radiotherapy has been based upon review of clinical studies evaluating orally-administered rucaparib. These studies showed rapid absorption of rucaparib, with peak plasma levels generally occurring within 1.5 to 6 hours postdosing.

The combination of RT with rucaparib may result in additive adverse events. This trial therefore aims to characterize the safety and tolerability of the combination of RT and rucaparib. Additionally, DNA repair-based correlates, such as HRR deficiencies, that we will study in this trial will yield invaluable insight into the rational construction of future studies of combination therapies with rucaparib. The

Breast Cancer Treatment and Outcomes Scale (BCTOS) is a validated instrument that will be used to assess patient reported outcomes (PRO) after treatment. The instrument was developed specifically for assessing PROs after lumpectomy and whole breast RT, and is divided into 3 subscales for cosmetic status, functional status, and pain ²⁰, Appendix B.

We are well-poised at MSKCC to conduct the proposed trial, given the large volume of women with TNBC treated annually with NAC, our experience in conducting clinical trials that integrate DNA repair-based assays and the unique resource of the MSKCC [name] lab, which has developed analytically-validated techniques to prospectively assess treatment response to PARP inhibition and RT.

In addition to TNBC, we also consider patients with hormone-receptor (HR+) positive breast cancer with high volume residual after NAC to be candidates for local-regional escalated therapy. In the Cortazar meta-analysis, HR+/Her2- patients with grade 3 disease were more likely to achieve pathCR compared to grade 1 / 2 , but non-responding grade 3 patients did demonstrably worse in terms of event-free survival²¹. A similar was finding was noted in a retrospective from MDACC examining patients treated with NAC, wherein high grade disease was an independent predictor of LRR²². Thus we propose including women with HR+/Her2- breast cancer with grade 3 disease and either 1) ypT3 or higher disease in the breast (>5 cm of residual disease) or 2) ypN2a or higher disease in the nodes, as candidates for escalated LRR treatment with concurrent PARPi.

4.0 OVERVIEW OF STUDY DESIGN/INTERVENTION

4.1 Design

This is a single-arm Phase I study conducted to determine the maximum tolerated dose of rucaparib administered concurrently with radiotherapy to the breast/chest wall +/- regional nodes in triple negative breast cancer patients with incomplete pathologic response following NAC.

The trial will be monitored using TITE-CRM as described in Section 14.0, and the dose level escalated or de-escalated accordingly. Subjects will receive rucaparib at their assigned dose level, beginning with Dose Level 0. Two patients will be enrolled to Dose Level 0, and DLTS will be assessed before starting the TITE-CRM dose escalation algorithm. Throughout the trial, at least 2 patients must be observed for their entire acute toxicity period (70 days) before any dose escalation is allowed.

Dose Escalation Schedule	
Dose Level	Dose of Rucaparib administered concurrently with radiation therapy to the breast / chest wall +/- regional nodes
Dose Level -4	200 mg QD
Dose Level -3	300 mg QD

Dose Level -2	200 mg BID
Dose Level -1	300 mg BID
Dose Level 0	400 mg BID
Dose Level 1	500 mg BID
Dose Level 2	600 mg BID

4.2 Intervention

Treatment will consist of rucaparib at one dose level (200 mg QD, 300 mg QD, 200 mg BID, 300 mg BID, 400 mg BID, 500 mg BID or 600 mg BID) concurrently with a 6-week course of radiotherapy and 4 additional weeks of maintenance rucaparib at the same dose level.

Radiotherapy will consist of 50 Gy in 2 Gy per fraction to the breast or chest wall with or without regional nodes plus a 10 Gy boost to the lumpectomy cavity, to a total dose of 60 Gy. A 10 Gy boost to the post-mastectomy scar is allowed at the discretion of the treating physician.

Weekly assessments for DLTs will be performed throughout RT, and every other week during the maintenance rucaparib period.

4.3 Correlatives

In an effort to identify the homologous recombination deficient (HRD) phenotype as a biomarker that can predict the sensitivity of TNBC tumors to study treatment, patients will undergo tumor specimen collection from their original diagnostic core biopsies as well as specimens from their post-neoadjuvant definitive surgery specimens if they are available. We will also evaluate presence of TILs in the pre-chemotherapy core specimens as biomarkers for local-regional and distant relapse.

Correlatives are further detailed in Section 10.0.

5.0 THERAPEUTIC/DIAGNOSTIC AGENTS

Rucaparib camsylate (formerly known as PF-01367338 and AG-014447) is an oral formulation with a molecular weight of 555.67 Daltons. Rucaparib tablets for oral administration will be supplied by Clovis. Please refer to the Investigator Brochure.

Drug Name:	Rucaparib
INN:	Rucaparib

Formulation:	Tablet; film coated 200 mg – blue, round, embossed with C2 250 mg – white, diamond, embossed with C25 300 mg – yellow, oval, embossed with C3
How Supplied:	200, 250mg and/or 300 mg strength (based on free base) in high-density polyethylene bottles or equivalent with child-resistant caps. Patients may receive 1 or more strengths.
Storage Conditions:	Store at room temperature, with no special storage conditions.

Study drug containers containing rucaparib tablets will be labeled according to national regulations for investigational products.

The investigator shall take responsibility for and shall take all steps to maintain appropriate records and ensure appropriate supply, storage, handling, distribution and usage of investigational product in accordance with the protocol and any applicable laws and regulations. Clinical supplies will be affixed with a clinical label in accordance with regulatory requirements.

6.0 CRITERIA FOR SUBJECT ELIGIBILITY

6.1 Subject Inclusion Criteria

1. Female, \geq 18 years of age.
2. Non-metastatic, histologically or cytologically-confirmed TNBC (defined as ER <1%, PR <1%, her-2/neu 0-1+ by IHC or FISH-negative or as per MD discretion), with evidence of residual disease in the breast or lymph nodes after neoadjuvant chemotherapy, at the time of definitive surgical treatment.
3. Non-metastatic, histologically or cytologically-confirmed hormone-receptor positive, Her2/neu negative breast cancer (defined as ER >1% or PR >1% AND Her-2/neu 0-1+ by IHC or FISH-negative, or as per MD discretion), with evidence of residual grade 3 invasive breast cancer AND either 1) >5 cm of residual disease in the breast OR 2) ≥ 4 axillary LNs in the axilla after neoadjuvant chemotherapy, at the time of definitive surgical treatment.
4. Definitive surgical treatment with breast-conserving surgery or mastectomy and axillary lymph node evaluation.
5. At least 6-month life expectancy, ECOG Performance status < 2.
6. Willingness to discontinue any cytotoxic chemotherapeutic agents and biologic therapy at least 2 weeks prior to the start of RT.

7. Adequate organ function (assessed within 30 days prior to initiation of protocol treatment, unless otherwise indicated) as follows:

Hematology

Absolute Neutrophil Count (ANC)	$\geq 1500/\text{mm}^3$
Platelet Count	$\geq 100,000/\text{mm}^3$
Hemoglobin	$\geq 9.0 \text{ g/dL}$ (after transfusion if required)

Renal Function

Creatinine	Serum $\leq 1.5 \text{ mg/dL}$ or Creatinine Clearance $\geq 45 \text{ mL/min}^a$
------------	--------------------------------------------------------------------------------------

Hepatic Function

Bilirubin	$\leq 1.5 \text{ mg/dL}^b$
Aspartate Aminotransferase (AST)	$\leq 2.5 \times \text{ULN}$
Alanine Aminotransferase (ALT)	$\leq 2.5 \times \text{ULN}$

ULN = upper normal limit of institution's normal range

- a. If calculated creatinine clearance is $< 45 \text{ mL/min}$, a 24-hour urine collection for creatinine clearance may be performed
- b. Subjects with documented Gilbert's disease may have bilirubin up to 2.5 mg/dL

8. Negative serum pregnancy test within 14 days prior to study treatment if a woman has child-bearing potential. Subjects of child bearing potential are those who have not been surgically sterilized or have not been free from menses for > 1 year.
9. Ability to swallow and retain oral medications.
10. Written informed consent obtained from subject and ability for subject to comply with the requirements of the study.
11. Female subjects of childbearing potential should be willing to use 2 methods of birth control or be surgically sterile, or abstain from heterosexual activity for the duration of study participation. Should a woman become pregnant while participating on study, she should inform the treating physician immediately.

6.2 Subject Exclusion Criteria

1. Gross residual tumor on imaging, or positive margins after breast conserving surgery that are un-excised, as radiation dose in the study will be limited to 60 Gy.
2. Complete pathologic response to NAC.
3. Receipt of PARP inhibitor prior to RT.
4. Pregnant or expecting to conceive within the projected duration of the trial, starting with screening visit through 180 days after the last dose of trial treatment.
5. Prior history of radiation therapy to the ipsilateral breast and/or regional nodes is not allowed (prior RT to other sites is permitted).
6. Patients with breast augmentation implants are excluded.
7. History of allergic reactions attributed to compounds of similar chemical or biologic composition to rucaparib.
8. Concomitant anti-neoplastic treatment is not allowed during protocol treatment and should be completed at least 2 weeks prior to commencement of protocol treatment, with resolution of associated acute toxicities. Bisphosphonates are permitted without restriction even during protocol treatment. Maintenance pembrolizumab is permitted during the protocol treatment.
9. Significant comorbidity: Patients with clinically significant and uncontrolled major disease or disorder that could exacerbate potential toxicities, confound safety assessments, require excluded therapy for management, or limit study compliance.
10. Ongoing therapy with other investigational agents. Patients may not be receiving any other investigational agents.
11. Unresolved toxicity from other agents. Patients with unresolved CTCAE v4.03 Grade 3 or greater toxicity from prior administration of another investigational drug and/or anti-cancer treatment are not eligible.

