9.4 Subsequent Therapies

Initiation of systemic therapy after completion of protocol treatment is at the discretion of the treating investigator, but should be delayed until no earlier than 30 days following completion to allow for assessment of acute toxicity and to allow full recovery for the sequelae of study treatment, unless such a delay would be harmful to the subject. Specifically, treatment with adjuvant capecitabine and/or pembrolizumab is allowed at the discretion of the treating physicians. Adjuvant endocrine therapy is allowed at the discretion of the treating physician and can be started before, during, or after protocol therapy.

Additional surgery is also at the discretion of the treating investigator but is not recommended for 30 days following the last RT session to allow evaluation of DLT and resolution of acute toxicity during that period. However, if delaying a surgical procedure would be harmful to the subject, surgery is allowed at the discretion of the treating investigator.

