9.5 Definition of Dose-Limiting Toxicity

Dose-limiting toxicity (DLT) will be defined as toxicities probably or definitely related to the study drug observed during the 70 days that include 6 weeks of radiotherapy and 4 weeks of maintenance rucaparib therapy, as follows:

- Confluent moist desquamation, defined as the presence of a single, contiguous region of moist desquamation that exceeds 25 cm² in area
- Absolute Neutrophil Count <1,000/mm³, with or without fever
- Platelet count <50,000/mm³
- Hemoglobin <8.0 g/dl
- Any ≥ Grade 3 non-hematologic toxicity by the NCI CTCAE version 4.03, not including Grade 3 ALT/AST elevation provided bilirubin and alkaline phosphatase meet criteria in Section 11.2
- Any toxicity requiring a RT dose delay exceeding 5 business days

Toxicities meeting this definition and occurring during the observation period of 10 weeks (70 days) will influence the dose level assignment of the TITE-CRM algorithm if these toxicities are deemed probably or likely related to study therapy.

Sites should contact the coordinating center as soon as possible (within one business day) when a DLT occurs or seems imminent. Sites should call [name] [name], and send an email to [name] [name] and study coordinator.

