9.6 Concomitant Treatment and Supportive Care Guidelines

Prior and subsequent systemic therapy is allowed, with a 2-week washout required for all anti-cancer agents, including cytotoxic chemotherapeutic agents, immunotherapy, biologic therapy, and targeted therapies. There are no limitations on the type or number of prior regimens.

Bisphosphonates are permitted without restriction even during protocol treatment.

No surgery is to be performed while the patient is receiving protocol therapy. At least three weeks must elapse since completion of surgery before initiation of protocol therapy.

Any medication or vaccine including over-the-counter and prescription medicines, vitamins, and herbal supplements that the subject is receiving at screening up to the week 10 visit should be recorded in source documents and case report forms. Administration dates (start and end dates), dose, and frequency will be recorded. Any change in concomitant therapy during the study period will be recorded.

Subjects should receive the best supportive care and treatment during the study as appropriate, including transfusion of blood and blood products, oxygen therapy, nutritional support, intravenous fluids, and treatment with appropriate medications (antibiotics, antiemetics, antidiarrheals, and analgesics, etc.).

Questions regarding prior or concomitant therapy should be directed to the Principal Investigators.

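### Section 6.2(8) permits pembrolizumab during protocol treatment, 6.1(6) and 9.6 do not, and the DLT analysis does not separate patients who receive it

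*Combined protocol and SAP*

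**What the plan says.** Four places bear on pembrolizumab.

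- Section 6.2, item 8, sets a general bar: "Concomitant anti-neoplastic treatment is not allowed during protocol treatment and should be completed at least 2 weeks prior to commencement of protocol treatment". It then makes two exceptions, bisphosphonates and a last sentence that reads "Maintenance pembrolizumab is permitted during the protocol treatment".
- Section 6.1, item 6, requires "Willingness to discontinue any cytotoxic chemotherapeutic agents and biologic therapy at least 2 weeks prior to the start of RT". It gives no exception.
- Section 9.6 allows prior and subsequent systemic therapy, "with a 2-week washout required for all anti-cancer agents, including cytotoxic chemotherapeutic agents, immunotherapy, biologic therapy, and targeted therapies". Its one stated exception is "Bisphosphonates are permitted without restriction even during protocol treatment".
- Section 9.4 covers systemic therapy started after protocol treatment. Such therapy "should be delayed until no earlier than 30 days following completion to allow for assessment of acute toxicity", unless waiting would harm the patient. It adds: "Specifically, treatment with adjuvant capecitabine and/or pembrolizumab is allowed at the discretion of the treating physicians".

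Section 9.5 defines a DLT through "toxicities probably or definitely related to the study drug observed during the 70 days". Later in the same section, the events that drive dose assignment are those probably or likely related to study therapy. Section 14.0 fits a one-parameter model of toxicity on dose and plans analyses over all patients and by dose cohort. It does not mention pembrolizumab. Section 9.6 does require concomitant drugs to be recorded, with dates and doses, from screening to week 10.

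**The concern.** Two things are at stake.

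The first is eligibility. Section 7.0 opens the trial to several sites, and Section 3.1 describes pembrolizumab as having changed the treatment of early TNBC, so candidates already on it are foreseeable. Sites that read different sections would enrol different patients.

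The second is the primary endpoint. Apart from a carve-out for liver enzymes, any non-hematologic event of Grade 3 or higher that is attributed to study treatment is a DLT under 9.5. The model has no term for a second drug. An event caused by pembrolizumab but attributed to study treatment would be read as an effect of the rucaparib level. A rucaparib event blamed on pembrolizumab would not be counted. No rule says how to attribute an event when both are given. Attribution is already hard: pneumonitis is an anticipated radiation toxicity in 11.1 and a rucaparib event of special interest in 17.2.

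**Working it through.** **Step 1: the passages side by side.** Take a woman on maintenance pembrolizumab who would continue it through radiotherapy.

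| Section | Result for this patient |
|---|---|
| 6.2(8) | Permitted by a named exception |
| 6.1(6) | Not met, if pembrolizumab is classed as a biologic; no exception |
| 9.6 | Not met; immunotherapy is named, and only bisphosphonates are excepted |
| 9.4 | Not engaged; it concerns starting therapy after protocol treatment |

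The conflict is between 6.2(8) and the pair 6.1(6) and 9.6.

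**Step 2: reproducing the plan's figure.** In Table 2a, Scenario 4, level -2 has the true 30% DLT rate and is selected with frequency 0.419. A lower level is selected with frequency 0.025 + 0.236 = 0.261.

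I simulated a TITE-CRM with inputs from Section 14.0: the revised expected toxicities (20, 30, 40, 50, 62, 70, 76%) as prior estimates, a 30% target and 23 remaining patients. Assumed, because the documents do not state them: a power model with a N(0, 1.34) prior and a start at level -2.

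Without the cap rules this selected level -2 in 41.8% of 1,500 trials, against 41.9% stated. The one-parameter logistic form that Section 14.0 names gave 35.2%, so I kept the power model. The match is partial. Amended Scenarios 1, 2, 5 and 6 miss by more than 2 points, so I use only Scenario 4.

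**Step 3: adding pembrolizumab DLTs.** The documents give no share of patients on pembrolizumab and no added DLT risk, so both are varied. Three set-ups were run:

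- A: no cap rules, 1,500 trials. The added risk applies to patients without another DLT, so the rate at level -2 is 0.30 + 0.70 × share × added risk. For 5 points and half exposed this is 0.30 + 0.70 × 0.5 × 0.05 = 0.3175; for 10 points it is 0.335.
- B: cap rules and the two-patient escalation rule, 800 trials. The rate is 0.30 + share × added risk, giving 0.325 and 0.35.
- C: cap rules, 2,000 trials, with the rate as in B.

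Percentage of trials selecting a level below -2:

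| Assumption | A | B | C |
|---|---|---|---|
| No added risk | 29.5 | 25.8 | 29 |
| +5 points, 50% of all 23 | 37.3 | 38 | not run |
| +10 points, 50% of all 23 | 47.4 | 52 | 50 |
| +10 points, 70% of all 23 | not run | 62 | 58 |
| +10 points, 50-70% use, last 11 patients only | not run | not run | 39-43 |
| +20 points, all 23 | 84.6 | not run | not run |

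Monte Carlo error is about 1.3 points in A and 1.7 in B; in C it is at most √(0.25/2000) = 1.1 points. None of the set-ups carries the seven patients already treated.

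**Step 4: what counts as below.** The table takes the pembrolizumab-free MTD as the truth. With +10 points and 70% use, Scenario 4 rates become 20 + 7 = 27% at level -3 and 30 + 7 = 37% at level -2. Level -3 is then nearer to 30% (3 points away against 7). In set-up C it accounts for 40 of the 58 points. For the patients actually treated, those selections are correct.

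**The case against.** Section 6.2(8) states its exception in the same item as its bar, so a reader can say that the specific permission governs. The 9.6 washout sentence opens with prior and subsequent therapy, so it need not reach concurrent use. Section 6.1(6) does not name pembrolizumab or immunotherapy. These readings are available, but the text does not settle on them: 9.6 repeats the bisphosphonate exception and omits the pembrolizumab one, and 6.1(6) has no exception.

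A reader might infer that 9.4 is a further contradiction, since it names pembrolizumab and asks for a 30-day delay. It is not one. It governs initiation after protocol treatment, a different situation from continuing maintenance, and it waives the delay where waiting would be harmful.

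On the endpoint, the attribution filter is real. Events judged only possibly related are tabulated under the Section 14.0 safety analysis but are not DLTs under 9.5. Pembrolizumab toxicity therefore lowers the MTD only where it is attributed to study treatment, and the opposite error is also possible. If concurrent use is intended, the declared dose is the MTD for the treated mix of patients and not a mistake. All of this stands, and it limits the claim to a possibility of unknown direction and size.

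**Conclusion.** The eligibility conflict between 6.2(8) and 6.1(6) with 9.6 is in the text and needs correcting. Section 9.4 needs only consistent wording.

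The effect on the MTD is conditional. On the assumed inputs, selection below the pembrolizumab-free MTD in Scenario 4 goes from about 26-30% to about 37-38% for a small effect and about 47-52% for a moderate one with half of patients exposed throughout. It is about 39-43% if only the last 11 patients are exposed. Stronger assumptions give more.

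A reader might infer that the MTD will be pushed too low in most trials, because pembrolizumab use falls in later patients at lower doses. The documents do not support that. They give no rate of use and no DLT rate, and they do not say when the permission was added. They do show that the first seven patients were at levels 0 and -1 and that the lower levels came afterwards, so such alignment is possible but not established. What holds is narrower: the MTD cannot be interpreted without knowing who received pembrolizumab and how their events were attributed.

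**What to change.** 1. Reconcile 6.1(6), 6.2(8) and 9.6 into one statement on pembrolizumab during protocol therapy, and align 9.4 with it. Which rule applies is for the sponsor to decide.
2. Use a single attribution wording in 9.5, in place of the two now there, and state how it applies when pembrolizumab is given concurrently.
3. In Section 14.0, tabulate DLTs by concurrent pembrolizumab use at each dose level.
4. Label any sensitivity posterior that omits or adjusts for exposed patients as exploratory. With 23 remaining patients over up to seven levels, it would be too imprecise to carry a conclusion.

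The cost is protocol wording and one table. The data are already collected under the concomitant medication rule in 9.6.
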